Building on an FRSQ-funded pilot study, we received CIHR support in 2006 to create the CCC, which is actively recruiting at 13 sites across Canada [see attached Protocol Summary; Summary of Progress]. The primary objective of this study is to determine the effect of HAART on liver disease progression in HCV-HIV co-infection. We are evaluating the contributions of important social factors, toxicities and immunologic factors that may modify fibrosis progression rates. The study is recruiting a total of 950 HIV+ adults with HCV infection. After initial evaluation, follow-up visits occur every 6 months. Medical information is collected using standardized questionnaires. Detailed information on demographics, substance use, risk behaviors and treatment history and blood samples is obtained. Plasma, serum and PBMC samples are stored for future viral, pathogenetic and immunologic studies. We are proposing to use the CCC as a platform to carry out the studies in the present proposal.

Recruitment Statistics [see also: APPENDIX 4]

As of the end of February 2008, 424 patients have been recruited from 11 centres. Two additional sites have recently opened. The average monthly recruitment has been 5 patients/site. With 13 sites, it is anticipated that by September 2008, 875 patients will be enrolled and that cohort will be fully recruited in 8-10 months. There have been 21 deaths and 7 withdrawals from study. Despite the social barriers faced by our participants, only 17 (4%) have been lost to follow-up. *Thus we have clearly demonstrated the feasibility of maintaining a cohort study with a population of patients that is traditionally considered difficult to follow.* There is significant variability in the population to allow for the selection of sufficient numbers in various groups to be able to perform well-controlled studies of potential biomarkers (i.e., 63% on HAART, 10% initiating HAART/year, 20% with liver biopsies).

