Biomarker Discovery for HIV–HCV Most biomarker programs focus on a single disease. Our attempt to define serum biomarkers associated with progression of liver disease in HIV–HCV co-infection is quite novel. However, it will likely be complicated by the intrinsic variability of the two underlying conditions and the varied therapeutic interventions used. Although the SELDI TOF MS platform is ideally suited to this type of complex situation, we will still need to exercise great care in selecting both patients and controls (see below). The stages of any biomarker program are Discovery, Validation and Identification. We will approach this complex problem in three general Phases.

Phase 1: Our initial **Discovery** effort will focus on otherwise ‘healthy’ HCV mono-infected controls and HIV-HCV co-infected patients with preserved CD4 cell counts (>350 cell/ul) and suppressed HIV RNA (< 50 copies/ml for at least 6 months on stable HIV treatment). Both groups will have evidence of replicating HCV (RT-PCR RNA+). Patients with other causes of liver disease or co-morbidities (i.e., current alcohol or drug use, Hepatitis B, TB) or prior/current HCV treatment will be excluded. This strategy should minimize potential “noise” in the serum proteome arising due to HIV-related immunosuppression and comorbidities (see detailed patient selection methods below).

Phase 2: Validation studies will be conducted with the groups above but in greater numbers (50-100 per fibrosis category) to confirm the validity of candidate biomarkers and guide prioritization efforts for biomarker **Identification** (see Sample Size Justification below). As samples accrue in our CIHR-funded archive, we will also have the opportunity to apply SELDI analysis to small numbers of serial samples from individual patients (e.g., with repeated biopsies). These sample sets may provide further validation of candidate biomarkers and/or biomarker patterns.

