Patient Selection To address our first hypothesis, primary analyses will focus on identifying biomarkers associated with fibrosis that are present in both HCV+ and HIV/HCV-co-infected persons. The gold standard for comparison will be the grade of fibrosis assessed on liver biopsy using the Batt and Ludwig scoring system. In this classification, those with minimal portal fibrosis or no fibrosis are scored as F0-F1, periportal fibrosis as F2, bridging fibrosis as F3 and cirrhosis as F4. In order to facilitate recruitment of appropriate subjects, the database of the CCC will be queried. Individuals having undergone a liver biopsy and who have stored serum samples within one year of the biopsy will be selected for study. We will use the fibrosis scores provided by the local site pathologist to select subjects. Standard semi-quantitative scores are used at all centres. The reports from all biopsies performed will be converted to the Batt and Ludwig scoring system for the purposes of analyses [see attached Histologic Grading of Liver Biopsies; APPENDIX 3]. In order to validate the biopsy readings, which may vary due to the expertise of the local pathologist, biopsy slides for all subjects in Phase 1 will be re-read by a single pathologist experienced in liver histology at the McGill University Health Centre. This pathologist will read all biopsies blinded to co-infection status, clinical and proteomic data. HCV mono-infected controls undergoing liver biopsy as part of routine care will be recruited through the RVH Hepatology and Infectious Diseases HCV clinics. Serum samples within one year of liver biopsy will be obtained after informed consent and stored frozen until analyzed.

SELDI Data Analysis-Discovery Previously frozen (–80°C) but never thawed serum samples within one year of liver biopsy will be studied initially. In order to ensure blinding in the SELDI analyses, samples will be aliquoted and coded in [name] laboratory and sent to [name] where SELDI spectra will be collected without knowledge of the fibrosis stage or diagnostic group. Discovery studies (Phase 1) will focus on HIV co-infected and HCV mono-infected groups at the extremes of the range of fibrosis (i.e., advanced fibrosis/cirrhosis (F>3) vs. minimal fibrosis (<F2)). Initially, we will study 10

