sera per fibrosis category and diagnostic group (total= 40 patients). In addition to simple across-group and across-category comparisons (ANOVA), correlations between the degree of fibrosis (biopsy scores) and individual biomarker peak intensities will be analyzed by Spearman rank-order correlation. Analyses according to fibrosis stage will be made overall and stratified by HCV-HIV co-infection status. Individual biomarkers that make unusually large contributions to the CART algorithms generated will be targeted for identification at this stage. We will focus on optimal samples for discovery and validation work. Once candidate biomarkers have been validated and identified, we will test intentionally ‘mishandled’ (e.g., repeated freeze-thaw) to assess the robustness of the each biomarker.

SELDI Data Analysis–Validation Larger numbers of sera will be separated by fibrosis category: minimal fibrosis (F0-1), mild fibrosis (F2), moderate fibrosis (F3), severe fibrosis/cirrhosis (F4) to assess the discriminatory ability of the individual biomarkers or biomarker patterns (n = 50-100 per fibrosis category and infection group). Ideally, equal numbers of patients will be studied in each of these groups. Although it may be more difficult to recruit individuals at the extremes (F0-1, F4), we observed the following distribution of fibrosis scores: 13 (28%) with F0-F1; 14 (35%) with F2, 10 (22%) with F3 and 9 (20%) with F4 among the 46 patients evaluated in our APRI validation study[47]. These data suggest that we should have a fair distribution across stages of fibrosis. If we find that scores are not evenly distributed, we may regroup stages to achieve groups of comparable sizes for analysis. The intensities of individual biomarker peaks and biomarker profiles will be compared within and between mono-infected and co-infected subjects as outlined above. All biomarkers making important contributions to distinguishing between groups and/or fibrosis categories will be confirmed by MALDI TOF MS and identified using a range of immunologic and mass spectrometric techniques (e.g.: EIAs when commercial kits exist or can be built easily, immunoprecipitation, Edmond sequencing, MS/MS).

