samples). It is in **Phase 3** studies that findings can be further validated through extensive analysis with other sample sets or control groups in addition to protein/peptide identification.

Feasibility Of 424 patients currently enrolled in the CCC, 53% are on HAART (with HIV RNA<50 copies/ml and CD4> 350) of whom 20% have undergone liver biopsy. Thus, we presently have sufficient samples to conduct Phase 1 studies in the co-infected. The full cohort is actively recruiting and is expected to reach its target by December 2008. Extrapolating from the currently enrolled patients, we expect 150-200 eligible subjects available for study. HCV mono-infected will be recruited retrospectively (through database review) and prospectively through the RVH HCV clinics which perform on average \approx 175 biopsies/yr. Thus the number of samples we require represents about 40% of available patients.

General Data Analyses Assessment parameters for the accuracy of proteomic biomarkers for the detection of significant hepatic fibrosis and cirrhosis will be calculated as shown in the simplified example in the table below. SAS PROC LOGISTIC (V.8.02; SAS Institute, Cary, NC) will be used to calculate AUROCs. Standard errors for the AUROC will be calculated according to Hanley and McNeil.[91] Primary analyses will group HIV co-infected and mono-infected subjects together according to level of fibrosis. We will also calculate the parameters for HIV co-infected and mono-infected separately. In addition, we will analyze promising candidate biomarkers combined with other markers of fibrosis that we are studying in parallel ongoing projects (e.g. HA, SHATA, APRI etc.).

Table 1. Diagnostic characteristics comparing proteomic biomarkers with liver biopsy scores

		Stage of HCV on Liver Biopsy	
		No Fibrosis/No Cirrhosis	Significant Fibrosis/cirrhosis
Proteomic biomarker	+	a (true positive)	b (false positive)
	-	c (false negative)	d (true negative)

Sensitivity = $a/a+c$; Specificity = $d/b+d$; Positive predictive value = $a/a+b$; Negative predictive value = $d/c+d$

IX. ROLES OF THE INVESTIGATORS

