APPENDIX 4.**HIV-HCV Cohort Site Recruitment Statistics**

Clinic Site	Total HCV pts followed	Number expected to recruit	Number Recruited to Date (Feb 2008)	% With biopsy
MCI	150	120	131	16
MGH	120	80	45	10
NDH/ CHUM	140	100	130	15
QL/EM	200	150	11	10
Ottawa	300	150	20	20
Toronto	87	60	24	52
Hamilton	100	50	0	60
Calgary	143	100	37	12
Vancouver	350	150	20	5
Halifax	57	50	2	10
Windsor	30	20	4	5
TOTAL	1677	1030	424	20

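### The 150–200 eligible co-infected subjects do not follow from the protocol's own rates, which give about 100 before exclusions: too few for 50–100 per fibrosis category

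*Protocol*

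**What the plan says.** Section VIII, Feasibility, describes the 424 patients then enrolled: "53% are on HAART (with HIV RNA<50 copies/ml and CD4> 350) of whom 20% have undergone liver biopsy". It then projects to the full cohort: "Extrapolating from the currently enrolled patients, we expect 150-200 eligible subjects available for study". The cohort target is in Section IV: "The study is recruiting a total of 950 HIV+ adults with HCV infection".

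Section VI defines the Phase 1 groups by preserved CD4 count and suppressed HIV RNA. It excludes other liver disease or co-morbidity ("current alcohol or drug use, Hepatitis B, TB") and prior or current HCV treatment. Phase 2 uses the same groups in larger numbers. Section VIII, Patient Selection, adds that stored serum must fall within one year of the biopsy.

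The Validation paragraph of Section VIII uses four fibrosis categories with "n = 50-100 per fibrosis category and infection group". It reports 13, 14, 10 and 9 of 46 patients in F0–F1, F2, F3 and F4, and allows stages to be regrouped if the scores are uneven. The sample size section repeats 50–100 per stage in both infection groups but totals this as 200–400 samples.

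**The concern.** The 150–200 is presented as an extrapolation from current enrolment, so it should be reproducible from the two percentages beside it and the cohort target. It is not. The viral load and CD4 restriction cannot be set aside to rescue it, because Phase 2 keeps the Phase 1 groups.

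Co-infection is the population the proposal is about. Aim 3 compares co-infected with mono-infected subjects at similar fibrosis stages, so it depends on the number of co-infected subjects in each stage. If the pool is a half to two-thirds of what is claimed, that comparison has far less power than the sample size section implies. Section XI (Strengths and Limitations) repeats the assurance that enough patients can be recruited; its fallback of recruiting at other centres is offered for the mono-infected controls.

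**Working it through.** **Inputs.** Enrolled 424, share meeting the HIV criteria 53%, share of those biopsied 20% (Feasibility). Cohort target 950 and 63% on HAART (Section IV). Expected recruits 1,030, patients followed 1,677, and site biopsy percentages (Appendix 4). Fibrosis split 13/14/10/9 of 46 (Validation; the text prints 35% for 14/46, which is 30%, so the counts are used here).

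**1. The stated range.** Eligible = cohort × share meeting criteria × share biopsied.

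- Now: 424 × 0.53 × 0.20 = 44.9
- At target: 950 × 0.53 × 0.20 = 100.7
- Using 1,030 expected recruits: 1,030 × 0.53 × 0.20 = 109.2
- Using 63% on HAART: 950 × 0.63 × 0.20 = 119.7

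None reaches 150. Working backwards, 150–200 needs a biopsy rate of 150/503.5 to 200/503.5 = 30–40%, or a cohort of 150/0.106 to 200/0.106 = 1,415–1,887.

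**2. Where the range could come from.** Leaving out the 53% gives 950 × 0.20 = 190. Applying both rates to all patients followed gives 1,677 × 0.53 × 0.20 = 178. Both lie in the range, so the documents do not settle its origin. Neither is the eligible cohort.

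**3. Sensitivity to the biopsy rate.** Weighting the Appendix 4 site percentages by recruited patients gives 68.4/424 = 16.1%; weighting by expected recruits gives 173.9/1,030 = 16.9%. Then 950 × 0.53 × 0.161 = 81 and 950 × 0.53 × 0.169 = 85.

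**4. Subjects per stage.** Pool × 13/46, 14/46, 10/46, 9/46:

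| Pool | F0–F1 | F2 | F3 | F4 | Even split |
|---|---|---|---|---|---|
| 101 | 28 | 31 | 22 | 20 | 25 |
| 85 | 24 | 26 | 18 | 17 | 21 |
| 81 | 23 | 25 | 18 | 16 | 20 |

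**5. Against the requirement.** Four categories × 50–100 = 200–400 co-infected subjects. If 200–400 is instead the total for both infection groups, the need is 200/8 to 400/8 = 25–50 per co-infected cell. With 101 subjects on the observed split, no cell reaches 50, and F3 and F4 miss 25 as well.

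**6. Power.** The sample size section gives 30 per group at low variance and 113 at high variance for a 1.5-fold difference, 80% power, alpha 0.05. It does not state the mean used. A mean of 3 (difference 1.5) with SD 2 or 4 reproduces both figures: a two-sided two-sample t-test has 81% power at 30 (SD 2) and 80% at 113 (SD 4). On the same assumptions:

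| n per group | SD 2 | SD 4 |
|---|---|---|
| 20 | 64% | 21% |
| 25 | 74% | 26% |

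**The case against.** **The Phase 2 total is ambiguous and regrouping is allowed.** This is fair. If 200–400 covers both infection groups, about 101 co-infected subjects just meet the minimum total. They do so cell by cell only with an even split, and on the reported split F3 and F4 still fall short. Regrouping into two categories could give about 50 each, but it gives up the four-stage comparison.

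**The 20% might describe the whole cohort.** Section IV does give 20% with biopsies cohort-wide, and 950 × 0.20 = 190. That would count biopsied patients before the viral load and CD4 restriction, so they would still not be the eligible subjects.

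**More biopsies may accrue.** Follow-up is six-monthly, 10% start HAART each year, and Phase 2 runs in year 3. A reader might infer that about 100 is a ceiling; the documents do not show that. Nor do they give a rate of new biopsies that would close the gap, and the sentence claims to extrapolate from current patients.

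Three further inferences are tempting but unsupported:

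- *That 16% should replace 20%.* Feasibility states 20% for the restricted subgroup itself. Appendix 4 describes unrestricted patients, includes a site with 60% biopsied and none recruited, and lists 11 sites where Section IV has 13. The 81–85 is a sensitivity figure only.
- *That co-infected accuracy estimates rest on 20–25 subjects, or about ±14 points at a sensitivity of 0.85.* Table 1 is a two-category analysis and the primary analysis pools both infection groups. If significant fibrosis means F2–F4 (the text does not define it), 101 × 33/46 = 72 positives give about ±8 points; if F3–F4, 101 × 19/46 = 42 give about ±11. Only the cirrhosis estimate in co-infected subjects alone rests on about 20.
- *That Phase 1 lacks samples.* This needs "advanced fibrosis/cirrhosis (F>3) vs. minimal fibrosis (<F2" to mean F4 only, giving 45 × 9/46 = 9 against 10 needed. The 95% Wilson interval for 9/46 is about 11–33%, or 5–15 of 45, so a shortfall is not established. If F3–F4 is meant, about 19 are available.

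**Conclusion.** The 150–200 is wrong as an extrapolation from the figures given. The protocol's own rates support about 100 at full enrolment and about 45 now. The exclusions for alcohol or drug use, hepatitis B, TB and HCV treatment, and the one-year serum window, are not in the stated product; their effect cannot be sized from the document, but they can only lower the count.

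From that pool, 50–100 co-infected subjects per fibrosis category is not attainable. The shortfall against the lower limit of 50 is about 19–30 subjects per stage, and F3 and F4 also fall below 30. This conclusion rests on three assumptions: the cohort reaches 950, the 53% and 20% hold in later recruits, and the 13/14/10/9 split (46 patients, so imprecise) applies. An even split would still give only 25 per stage. The power figures additionally assume a mean of 3. The consequence falls mainly on the four-stage co-infected comparison and Aim 3, and much less on the pooled primary accuracy analysis.

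**What to change.** 1. In Feasibility, replace 150–200 with about 100 before exclusions. Give 80–85 as a sensitivity figure if the Appendix 4 site biopsy rates apply within the subgroup. Confirm the eligible count with a query of the cohort database that applies every exclusion and the serum window.
2. Reconcile the Validation paragraph (200–400 co-infected subjects) with the sample size section (200–400 samples in total), and state the number per fibrosis category and infection group once.
3. State the attainable co-infected number per stage with its power, and state the mean and SD assumed.
4. Label the four-stage co-infected comparison under Aim 3 descriptive, unless stages are regrouped as the Validation paragraph allows; if so, fix the grouping in advance.
5. Bring the recruitment assurance in Section XI (Strengths and Limitations) into line.

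The cost is protocol wording and one database query. No extra patients are needed, but the stated figures become less favourable.

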Based upon the experience in the [name]/[name] laboratory, as well as the small but growing literature describing the application of SELDI and related technologies to clinical hepatology, we are confident that the work we propose will reveal new and discriminatory biomarkers in HCV-HIV co-infected subjects. As noted above, many clinical proteomics projects stumble over the issues of access to patients and the collection of adequate patient information. Use of the structured data and sample collection afforded by the HCV-HIV cohort will ensure this is not a problem. Although it is impossible to predict what types of biomarkers will be identified in a discovery program such as this, we anticipate that: a) several biomarkers will need to be combined in order to achieve high sensitivity and specificity for liver disease status. It is certainly possible that the optimal combination will include existing surrogate markers (eg: APRI) as well as new biomarkers discovered in the course of this program and that the optimal biomarker combination may vary with the stage of disease; b) unlike existing scoring systems for liver disease, it is likely that individual serum biomarkers or combinations of biomarkers will be identified that can provide prognostic information rather than simply acting as markers for current disease status at the time of testing; and c) at least some of the new serum biomarkers identified may be informative regarding the underlying immunopathology of HCV-HIV co-infection, giving insights into novel preventative or therapeutic strategies to mitigate disease progression.

XI. STRENGTHS AND LIMITATIONS

This proposal is an example of the type of translational research that can be developed from a population-based cohort study. It provides for a synergistic collaboration between two investigators, combining expertise in clinical study design and statistics with serum proteomic methods. It will serve as an excellent training opportunity for a new generation of HIV-HCV researchers. As discussed above, a major challenge in proteomic studies is that heterogeneity among subjects and the presence of confounding variables can lead to artifacts in the assignment of a phenotypic response to the disease process under study. Failure to consider variations in sample collection, storage and quality can further compromise the ability to identify protein profiles that correspond to specific histologic phenotypes.[92] Thus, the clear advantage to our study is our ability to select samples from a population that is extremely well-characterized, having instituted strict patient selection criteria and rigorous sample collection and storage procedures. We have presented a step-wise discovery program. Phase 2 studies are obviously dependent on success in Phase 1. A growing body of literature supports that the population proteomics approach will be fruitful for studying fibrosis in HCV.[83, 85-88] Indeed, our studies in mono-infected subjects will serve to confirm (refute) work published in this area to date, as well as extend it by identifying all of the candidate biomarkers. Our own pilot data support our ability to detect potential biomarkers that can distinguish advanced fibrosis from minimal to no fibrosis in HIV-HCV co-infection using the techniques we are proposing. We already have sufficient samples to perform Phase 1 studies among HIV-HCV co-infected persons. Our current data support our ability to recruit enough patients for study once the full CCC has been enrolled. Although a considerable number of HCV mono-infected controls must be recruited, we are confident that we can do this rapidly for Phase 1 studies. Given the large number patients evaluated annually in the clinics (n=175), we do not anticipate difficulties in recruiting sufficient controls for Phase 2. However, if recruitment is lower than anticipated, we will extend recruitment to other centres. For example, several CCC co-investigators (e.g., [name], [name], [name]; see collaborators list) run large HCV mono-infection clinics. The advantages and disadvantages of the SELDI platform have been discussed in detail above. Although we have based our primary discovery program on SELDI, we do not intend to rely on a single platform for these studies. The recent acquisition of a high-throughput TOF/TOF by Drs [name] & [name] further mitigates against both the real and perceived limitations of SELDI.

XI. STUDY TIMELINES

A complete study timeline is provided in the Budget Justification. Briefly, in the first 4-6 months a protocol and consent forms will be prepared and submitted to the IRB for the HCV mono-infected patients. Study personnel will be trained. A data analyst will query the CCC database and link to sample repository for Phase 1 studies, as well as to create a database for HCV mono-infected study data and samples. We will recruit a post-doctoral health professional. The fellow will receive training in SELDI and proteomic techniques. HCV mono-infected controls will be recruited and phase 1 studies will be initiated by the end of the first year of the grant. In year 2, recruitment of HIV-HCV cohort participants and HCV controls for Phase 2 studies will continue. Analytic methods will be optimized and Phase 1 studies will be completed and analyzed. In the third year, Phase 2 studies will be performed and analyzed. Results will be presented at scientific meetings. Finally, in the last 6 months, we will plan future validation (Phase 3) studies and submit final results for publication. We envisage that protein identification efforts will begin by the end of the first year and continue through the second and third years of the study as new, discriminatory biomarkers are discovered among the lower abundance proteins.

XII. IMPLICATIONS AND FUTURE DIRECTIONS

While liver biopsy is currently accepted as the gold standard for evaluating cirrhosis, it is an imperfect one. The identification of protein biomarkers that reliably predict stages of fibrosis will have important implications for the study and care of HIV-HCV co-infected persons. By comparing HCV mono-infected with HIV-HCV co-infected persons we also hope to discover proteomic differences which will shed light on the pathogenesis of the accelerated disease course in HIV co-infected persons. If we are successful in this discovery phase, more detailed evaluations of the roles of different levels of immunity and HIV replication, as well as the roles of potential co-factors in driving fibrosis progression, will be explored. Furthermore, it will be important to understand if the proteomic biomarkers we identify are correlated with other described indirect and direct fibrosis markers and if proteomic markers are superior to or synergistic with these markers in predicting fibrosis. With multiple aliquots of serum and PBMCs, we are in a position to evaluate a wide range of biomarkers in parallel. In ongoing and planned studies, we will focus on studying various indirect (e.g., APRI, FIB-4) and direct (e.g., hyaluronic acid) markers in evaluating and following hepatic fibrosis. In addition, the Hepatology group at the RVH is acquiring a Fibroscan machine. We will be participating in validation studies in HCV mono-infected and co-infected patients and plan to co-enroll the subjects captured in the proteomics study. Our long-term goal is to identify candidate biomarkers that could be used longitudinally to study liver disease progression in population-based cohorts and eventually in the clinical setting. Specifically, we hope to prospectively determine their predictive value for clinical outcomes (e.g., ESLD and/or death from liver disease in HIV-HCV co-infection) and to study the role of biomarkers in assessing the effects of HAART and HCV therapy on liver fibrosis progression, accounting for other potential biologic and social factors. The wealth of longitudinal clinical and laboratory information and samples collected as part of the CCC places us in a unique position to realize these objectives in a well-characterized population.

XII. CONCLUSIONS.

